ATTOC was conducted in the context of in-patient substance abuse treatment and used a non-randomized, single-arm, prospective design [18] [see also Preliminary Studies section for our pilot studies]. Three residential, substance abuse treatment sites received the ATTOC intervention. Clinician behavior and client tobacco use was assessed pre- and post-intervention, and at a 6- month follow-up. On an organizational level, clinician beliefs about treating TUD became significantly more positive and clinician provision of NRT significantly increased post-intervention (verified by clients). On an individual level, significant post-treatment improvements were reported in: client willingness to quit and use of TUD treatments. Tobacco use rates among clients, however, were not significantly lower post-intervention. Several reasons could explain this but, most notably, clients remained at the clinic for a mean of 6-7 weeks and, thus, were exposed to an enhanced model of care for a short time. Also, and perhaps most important, subjects in the pre-post evaluations were different inpatient cohorts. Further, bupropion, varenicline, and combination NRT were not offered as treatment options, each of which is superior to nicotine patch [20]. Lastly, policy changes, including on-campus tobacco use, were challenging to implement in a residential treatment setting (although we have shown this is feasible [56]). While these data support the feasibility and impact of ATTOC on key barriers to cessation, studies – using a randomized design, tracking individual client outcomes, targeting out-client settings that provide sustained care, and promoting more effective medications are needed to fully evaluate the ATTOC model for addressing TUD among those with an SMI.

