Pilot Study to Improve Treatment of TUD in Philadelphia DoH Clinics: Drs. [name] and [name] completed a single-arm study to assess the effects of a training program in TUD treatment on clinician behaviors. The study was implemented in DoH clinics that primarily serve low-income, minority populations (e.g., 26% of clients below poverty line; 57% African American or Hispanic). In 9 months, 217 clinicians were recruited and completed a baseline assessment of "simple" (asking about tobacco use, advising cessation) and "complex" (providing medication, quit-line referral) TUD treatment behavior. Training, based on the ATTOC model, involved a clinic visit to provide instruction in TUD treatment, educational material, and discussions to address beliefs that may undermine the provision of TUD treatment, access to a training website, 3 reminder letters, and a follow-up visit to reinforce training. At a 2-month post-treatment assessment, clinician treatment of TUD increased for "simple" ($p=.04$; 11% improvement) and "complex" ($p<.001$; 30% improvement) behaviors [19]. This study demonstrates our ability to collaborate with the DoH to implement organizational change interventions within health clinics that assist primarily under-served communities.

Preliminary Data from Philadelphia DoH Mental Healthcare Clinics: Drs. [name] and [name] initiated the pilot clinician training program described above with community mental health clinics (CMHCs; <http://smokefreephilly.org/quit-now/for-mental-health-professionals/>). So far, we have recruited 167 mental healthcare clinicians from 10/40 agencies approached (25%) and followed the methods described above. While data collection is ongoing, our preliminary findings in the context of mental healthcare are similar to what we found in primary care, with upwards of a 14% increase in "complex" TUD treatment behavior (e.g., connecting clients to TUD treatment; $p = .02$). These data demonstrate the potential effects of ATTOC in Philadelphia community mental healthcare and show the feasibility of recruiting clinics for the proposed study.

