4.3 Rationale for Study Design

An alternative design would involve randomization of clients and providers within the agencies. Although that could avert potential confounds attributable to differences between agencies, we considered the risk of contamination – and, thus, a threat to internal validity – from such a design to be too probable. While an agency-level randomization may be subject to confounding as well, we will match the agencies on key variables before randomization to increase control over potential treatment confounds and we will use appropriate analytic models to account for this potential confounding (see Data Analysis). We also considered either: 1) not including a control arm; or 2) providing a more potent control arm, but considered the present design one that would allow for more convincing conclusions about the effects of ATTOC vs. current practice. Thus, we viewed the proposed design to be the ideal balance between internal and external validity.

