6.2 Study Intervention Phase

6.2.1 Overview of Interventions

Usual Care (UC): Sites randomized to UC will not receive an organizational intervention to address TUD treatment. To ensure standardization across UC sites, [name] and/or [name] will provide a 1-day training seminar that will include written materials describing recommended treatments for TUD to UC personnel consistent with established treatment guidelines. This minimal treatment condition was selected to facilitate the evaluation of the ATTOC training program on key outcomes relative to current clinical practice and organizational culture and climate. UC site personnel and clients will also be compensated for the time and effort required to complete assessments, which should also lower the risk for study withdrawal.

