ATTOC Intervention: ATTOC is implemented in a systematic 3-phase process with 10 steps (Table 2) to guide sites through cultural change and implementation of evidence-based practice. ATTOC is flexible to accommodate the unique needs, barriers, resources, and goals of an agency. Each organization begins at its own starting point based on what it has already accomplished (although, from our experience, most agencies are similarly not systematically addressing TUD at baseline), so the ATTOC intervention starts with diagnosis and proceeds to intervention and evaluation, consistent with ODT. Across the steps within the phases, 7 core strategies are used: 1) Meetings, calls, and video-conferences to prepare for and implement the intervention; 2) On-site consultation and technical assistance, including an Environmental Scan and training; 3) Formation of the agency's Tobacco Champion/Leadership to support culture and practice change, including the use of a "dashboard" assessment to provide performance feedback; 4) Implementation of the agency's change plan to achieve its Client, Staff, and Environmental goals; 5) Formal training/technical assistance in the treatment of TUD at the agency with ongoing monitoring, feedback, and coaching by champions; 6) Sustained consultations, including the use of the dashboard assessment to monitor organizational change and provide performance feedback to clinicians; and 7) Web-based support. The ATTOC intervention will be implemented over 9-months via 10 sessions (as in ongoing ATTOC initiatives): 2 in-person/on-site and 8 by video-conference (or teleconference) (see: <http://www.umassmed.edu/psychiatry/attoc.aspx>). Due to the fact that many community mental health clinics provide fee-for-pay service, the study has budgeted up to \$1,500 per site, depending on the need of the site. This compensation is meant to offset the cost associated with lost time and effort due to study participation on the part of clinic personnel.

6.2.2 Week 1

Usual Care (UC): Clinics will take part in a 1-day training session with [name] and/or [name].

ATTOC Intervention: Week 1 is a 3-day on-site technical assistance and training visit for clinic personnel. Site personnel are not required to attend the entire 3-days and training sessions are divided into blocks so that normal agency functions can occur. This visit involves the following components:

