7.1 Sample Size and Power Determination

For cluster-randomized designs, clinic is the unit of randomization and the unit of analysis is the individual. Power is reduced by variability among clinics, represented by the intra-class correlation (ICC), analogous to an R-squared. The size of the individual sample affects precision within clusters and certain outcomes are less susceptible to potential confounding vs. others (e.g., smoking rates vs. provider adherence) since they are more independent.

For Aim 1, the analysis will compare ATTOC to UC on weeks 36 (EOT) and 52 rates of adherence to guidelines for treating TUD. The sample size was determined by assessing the mean change in practice behavior detected in Guldish et al. [18]. Given the expectation from that trial that the UC mean level of practice will be 2.36 (SD=.87), the present sample of N=14 agencies (with 280 subjects) provides 80% power ($\alpha=.05$) to detect an effect if practice behavior increases by 0.32 (on a 5-point scale) if the ICC is 0. But if our ICC is .05, .10, or as high as .15, we have 80% power ($\alpha=.05$) to detect a difference between ATTOC and UC of 0.44, 0.54, and 0.62, respectively. If 15% of the personnel are lost-to-follow-up, we will have 80% power ($\alpha=.05$) to detect an effect if practice behavior increases by 0.34 for ICC=0, by 0.46 for ICC=.05, by 0.56 if ICC=0.10, and by 0.63 if ICC=.15. The effects of ATTOC were stronger at the 3-month follow-up (mean change of 0.51), vs. EOT [18], so the current power is adequate for both time-points. Likewise, because the client sample will be more than twice as large as the clinic staff sample, we will have greater than 80% power to detect differences using the measure of physician adherence collected from clients.

For Aim 2, the analysis will compare the rates of smoking cessation between the ATTOC intervention and UC at weeks 36 and 52. We can expect that UC cessation rate will be < 2% [18]. With 14 sites (n=700 clients, ITT), we have 80% power ($\alpha=.05$) to detect a difference between ATTOC and UC of 4% with an ICC=0. But if our ICC is .05, .10, or as high as .15, we have 80% power ($\alpha=.05$) to detect a difference between ATTOC and UC of 10%, 15%, and 19%, respectively, with 14 sites and n=700 client (ITT).

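### The control arm is described as current practice but receives a 1-day guideline training, and the statement that Aim 1 power is adequate rests on an uncontrolled change of 0.51

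*Combined protocol and SAP*

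**What the plan says.** Section 4.3 justifies the design as one that would allow "more convincing conclusions about the effects of ATTOC vs. current practice", and records that a stronger control was considered and not adopted.

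Section 6.2.1 withholds the organizational intervention from UC sites but, for standardization, states that study staff "will provide a 1-day training seminar that will include written materials describing recommended treatments for TUD to UC personnel". It continues: "This minimal treatment condition was selected to facilitate the evaluation of the ATTOC training program on key outcomes relative to current clinical practice". Section 6.2.2 (Week 1, Usual Care) repeats it: "Clinics will take part in a 1-day training session with ...". The Section 6 schedule also shows a UC entry at Week 1.

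For Aim 1, Section 7.1 writes: "Given the expectation from that trial that the UC mean level of practice will be 2.36 (SD=.87"). It gives detectable differences for 14 sites and 280 personnel at four ICC values, with and without 15% loss. It then notes that the source trial saw a larger effect at the 3-month follow-up (mean change 0.51) than at end of treatment, and concludes that power is sufficient at both assessments. Section 2.1 says of that source trial that it "used a non-randomized, single-arm, prospective design".

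**The concern.** Two statements claim something the design does not have.

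The first is the comparator. A study-delivered training day on guideline treatment is not what clinics do unprompted: Section 6.2.1 itself says that most agencies do not systematically address tobacco use at baseline. The treatment term therefore estimates ATTOC minus a 1-day training. If the training helps, this is smaller than the effect against untrained practice, and a null result could mean that both arms improved. A reader who relies on Section 4.3 would not see that.

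The second is the adequacy of power. A pre-post change in a trial without a control group has no control gain subtracted from it. It equals the expected between-arm difference only if UC staff do not change. That is a strong assumption when they are trained at Week 1, and the plan does not state it.

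**Working it through.** **Inputs.** 7 clinics per arm (Section 4.1); 280 personnel, so m = 280/14 = 20 per clinic, or 20 × 0.85 = 17 with 15% loss; SD 0.87; α = .05; 80% power; ICC 0, .05, .10, .15; reference change 0.51 (all Section 7.1 unless noted). Section 7.1 does not say whether the Aim 1 test is one- or two-sided; a two-sided test with 14 − 2 = 12 df reproduces its figures.

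**Step 1: reproduce the plan.**

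SE = 0.87 × √[2(1 + (m − 1)·ICC)/(7m)]

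Detectable difference = (t.975,12 + t.80,12) × SE = (2.179 + 0.873) × SE = 3.051 × SE

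Example, m = 20 and ICC .10: SE = 0.87 × √(2 × 2.9/140) = 0.177, and 3.051 × 0.177 = 0.540.

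| ICC | Plan, m = 20 | Computed | Plan, 15% loss | Computed |
|---|---|---|---|---|
| 0 | 0.32 | 0.317 | 0.34 | 0.344 |
| .05 | 0.44 | 0.443 | 0.46 | 0.462 |
| .10 | 0.54 | 0.540 | 0.56 | 0.555 |
| .15 | 0.62 | 0.623 | 0.63 | 0.635 |

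All eight agree to within rounding. The UC mean does not enter the formula. At ICC .05 the detectable difference is 0.443 whether that mean is 2.36, 2.46, 2.56 or 2.69.

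**Step 2: take 0.51 at face value (no UC gain).** 0.51 is larger than the plan's detectable differences at ICC 0 and .05, but smaller than those at ICC .10 (0.54) and .15 (0.62). Power is from the noncentral t distribution with 12 df and noncentrality 0.51/SE:

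| ICC | m = 20 | 15% loss (m = 17) |
|---|---|---|
| 0 | 99% | 98% |
| .05 | 90% | 87% |
| .10 | 75% | 73% |
| .15 | 63% | 62% |

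These figures use the follow-up value. The end-of-treatment change was smaller and is not given, so Week 36 power cannot be computed. At the same ICC it would be lower than shown.

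**Step 3: allow UC to respond to its training.** The documents give no UC gain. The values below are illustrative assumptions. They hold the total ATTOC gain at 0.51, so the contrast is 0.51 minus the UC gain.

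| Assumed UC gain | Contrast | ICC .05 | ICC .10 | ICC .15 |
|---|---|---|---|---|
| 0 | 0.51 | 90% | 75% | 63% |
| 0.10 | 0.41 | 74% | 57% | 46% |
| 0.20 | 0.31 | 50% | 36% | 29% |

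With 15% loss, the 0.10 row becomes 70/55/44% and the 0.20 row 47/35/28%. At ICC .05 the margin is small: 0.51 − 0.443 = 0.067 (or 0.51 − 0.462 = 0.048 with loss). A UC gain above that takes power below 80%.

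**The case against.** The training day is openly disclosed, is called minimal, and serves to standardize the control arm. UC sites receive none of the organizational intervention, which is what ATTOC is meant to test. A brief-training control is legitimate, and if the training helps, a positive result is conservative relative to untrained practice. UC S-KAP scores are collected throughout, so movement in both arms would be visible in the data. All of this stands, and it is why the point concerns naming and a power statement rather than the choice of control.

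Several stronger readings are tempting, but the documents do not support them:

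- **That 2.36 is an untrained mean and so undermines the Aim 1 figures.** Step 1 shows that the figures do not use it. A pre-intervention origin is a reasonable inference from the single-arm source, but Section 7.1 does not say so.
- **That the power section itself claims current practice as comparator.** It speaks only of UC; the wording is in Sections 4.3 and 6.2.1.
- **That the pilot gains in Section 2.2 (11%, 14%, 30%) predict the UC gain.** The scale of those percentages is not stated, the DoH pilot was itself single-arm and measured at 2 months, and the programme also had a website, reminder letters and a follow-up visit.
- **That the UC quit rate assumed for Aim 2 is compromised in the same way.** Nothing shows that a staff seminar raises client quitting.
- **That the cost analysis omits the seminar.** Section 7.2.1 sums all measured costs, including treatment costs, in both arms.
- **That the cessation resources in Section 5.5 further alter UC.** They are offered to clinics without distinction of arm.

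**Conclusion.** Wrong as written on two counts. First, the contrast is ATTOC versus usual care plus a 1-day guideline training; the claim to evaluate ATTOC against current practice cannot be met, because no arm is untrained. Second, the statement that Aim 1 power is adequate at both time points is unsupported. It borrows an uncontrolled change, it rests on the larger of two values, and even with no UC gain it fails at two of the plan's four ICCs (75% at .10 and 63% at .15; 73% and 62% with 15% loss).

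The Aim 1 detectable differences are correct. The power figures rest on a two-sided 12-df comparison, 20 (or 17) personnel in every clinic, and SD 0.87. The reductions for a UC gain rest on assumed gains and are not a forecast. If UC staff do not respond to the training and the ICC is .05 or less, power for a true difference of 0.51 is at least 87% even with 15% loss.

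**What to change.** 1. In the aims, Section 4.3 and Section 6.2.1, name the comparator as usual care plus a 1-day guideline training, and remove or reword the statements about current practice. The control arm itself need not change.
2. In Section 7.1, replace the adequacy sentence with power by ICC for the difference between ATTOC and trained UC. State where 2.36 and 0.51 come from (time point, and before or after intervention), and give the end-of-treatment change if it is available. Show power for UC gains of, for example, 0, 0.10 and 0.20, labelled as assumptions: 90%, 74%, 50% at ICC .05 and 75%, 57%, 36% at ICC .10.
3. In Section 7.2.1, report the UC change in S-KAP adherence from baseline to Weeks 36 and 52, with a confidence interval that allows for clustering by clinic, beside the arm contrast. This is descriptive, since a pre-post change also contains any time trend, but it lets a null result be read properly.

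The cost is wording and one additional estimate from data already scheduled. No new participants, visits or measures are needed. The downside is that the stated power becomes less favourable.

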6.3 Session Windows

Intervention treatment sessions for clinic personnel will occur +/- 1 week from the study timeline date to account for scheduling needs of clinics and trainers. In-person ATTOC sessions at Week 1 and 12 may be scheduled +/- 2 weeks from the study timeline date as travel arrangements must be made for the UCSF study team. If a personnel participant at an ATTOC randomized clinic is not available to attend any interventional study session (Weeks 1-36), the intervention will not be repeated for individuals.

Personnel participants who miss an assessment session or are unable to complete an assessment within the allotted session time are afforded a +/- 1 week study window to complete the assessments by phone. If there are extenuating circumstances that would cause personnel participants to miss a study session (e.g., end of an employment period), personnel sessions may be

completed earlier than the +/- 1 week session window. All client participant assessments will have a window of +/- 1 week to complete treatment and outcomes assessments for weeks 12, 24, 36, and 52. Participants may choose to complete the assessments in person or by phone.

Session windows may be extended with prior authorization from PI at his discretion. Session window extensions will not be considered reportable deviations.

6.4 Subject Withdrawal

Clinic personnel or client participants may choose to withdraw from the study at any time. They do this by providing verbal or written communication to this effect. Withdrawal from the study will not impact employment status (clinic personnel) or access to care (clinic clients) within the clinic. The Principal Investigator may withdraw subjects who violate the study plan, to protect the subject for reasons related to safety or for administrative reasons. It will be documented whether or not each subject completes the study. Subjects who withdraw early will be contacted to complete a final visit (Week 52) to collect final evaluations and assess adverse events.

To increase retention and adherence we will: 1) conduct interventions at the clinic; 2) conduct assessments during scheduled clinic visits or by phone; and 3) as is standard in TUD trials [65, 66], provide financial compensation for assessment completion. Although we expect that a small percentage of personnel and clients will leave their agencies, based on our past trials [71] and preliminary research with DoH clinicians [19], we expect that <15% of personnel and clients will withdraw from the trial or be lost-to-follow-up and ~85% of assessments will be completed, which exceeds past trials (e.g., [102]). As is advised in smoking cessation trials [101], intent-to-treat (ITT) will be used for Aim 2. Should, in the unlikely event, a CMHC withdraw from the trial, our time-line and prospective recruitment will allow replacement with a new CMHC.

7 Statistical Plan

All data are maintained on password-protected computers within a DMS that uses ORACLE and MS ACCESS to permit web-based real-time data entry, storage, and QA

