4.8 Study Endpoints

4.8.1 Primary Study Endpoints

For Aim 1, we will assess adherence to guidelines for treating TUD as done previously [18, 31, 72, 73]. This measure, developed by Delucchi et al. [103], assesses components of the USPHS guideline [20]. Items measure the rate of: asking clients about smoking, advising them to quit, providing assistance with quitting, and arranging visits to track progress. A total adherence score can be calculated [18]. We will supplement this measure with questions about the content, nature, and intensity (in terms of time) of behavioral counseling provided. Clinician adherence will be assessed from the client perspective as well, using the client version of this scale [105], EHR adherence data will be accessed (e.g., documenting smoking status, use of pharmacotherapy), and prescription data (provided and filled) will be accessed by CBH.

For Aim 2, smoking status is assessed using self-reported 7-day point prevalence and CO to verify self-report [66, 106], with abstinence=self-reported abstinence for >7 days prior to the weeks 36 and 52 assessment and a breath CO <8ppm at the time-point [98, 99]. Participants are assumed to be smoking if they self-report to be smoking at the time-point, do not provide self-report or CO data at the time-point, or provide a breath sample at the time-point that is >8ppm [93]. Secondary outcomes will also be assessed (e.g., smoking status at week 12, smoking rate [number of cigarettes/day]).

For Aim 3, client mental health will be measured using several indicators [107]. We will assess the frequency and duration of any illness-related in- client hospitalization (available through the EHR). Clients will complete the Revised Behavior and Symptom Identification Scale (BASIS-R), a 24-item assessment of mental health functioning [108] that yields a total score and subscale scores for: depression, interpersonal relationships, self-harm, emotional lability, psychosis, and substance abuse. The Short-Form Health Survey (SF-12) will assess physical and mental QOL [109, 110].

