For Aim 3, the analysis will use non-inferiority testing to compare mental health and QOL across ATTOC and UC at weeks 36 and 52. Standard statistical tests, which may yield a non-significant comparison of means or proportions, cannot be used to claim that the treatments are equal since "the absence of evidence is not evidence of absence". Among persons with SMI, the rate of psychiatric hospitalization nationally is 11.4% [114], which may represent UC (i.e., 88.6% of UC subjects will not have a hospitalization across the 52 weeks). One study found that 3.3% of clients with an SMI treated for TUD had a psychiatric hospitalization [48] or that 96.7% of clients treated for TUD did not experience a psychiatric hospitalization. We assume 14 sites (700 clients), with potential loss of 15% to follow-up, and assume approximately 90% non-hospitalization in the UC group. We will set our non-inferiority floor 20% below the US rate, which yields 80% power to detect non-inferiority if the ICC is as much as 0.15 (more power if ICC is less than 0.015).

A trial with smokers with an SMI reported baseline BASIS-R scores of 2.1 (SD=0.8) and SF-12 scores of 48.7 (SD=12.5) for the physical sub-scale and 27.8 (SD=12.9) for the mental sub-scale, which estimates UC [107]. Given the sample of 14 sites (700

clients) and potential 15% loss to follow-up, we have 80% power ($\alpha=0.05$) to detect non-inferiority if the results for the ATTOC arm differ from UC by as much as 0.19 on the BASIS-R, when ICC=0, and by 0.50 when ICC=0.15.

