7.2.1 Analysis of Outcomes of Interest

The effects of the ATTOC model on provider adherence to guidelines for treating TUD: We hypothesize that the ATTOC intervention will increase adherence to guidelines for treating TUD vs. UC. The outcome is continuous and the hypothesis will be tested by a treatment arm term in a mixed-models linear regression model that may include covariates. Mixed models may account for individual level clustering inherent in longitudinal studies and site level clustering. Outcomes of the analysis will be characterized by regression coefficients and confidence intervals. Significance will be determined from a z-score corresponding to the treatment variable. Although level of adherence at 36 and 52 weeks will represent our primary outcome variables, similar regression analyses will be performed for assessments at Weeks 12 and 24. Also, we can examine models of specific clinician practices (e.g., identifying smoking, recommending pharmacotherapy) and examine adherence from the client perspective and based on adherence data ascertained from the EHR.

The effects of the ATTOC model on client smoking: The hypothesized effect of treatment arm (i.e., the difference in quit rates between subjects receiving the ATTOC intervention or UC) will be tested by a treatment arm term in a mixed-models logistic regression model with covariates. Outcomes of the analyses will be characterized by odds ratios (e.g., odds of quitting smoking) and 95% confidence intervals. Although quit-rates at the end of 36 and 52 weeks will represent our primary outcomes, similar analyses will be performed for other assessments of quit rates (e.g., at Weeks 12 and 24). In addition, as many participants will fail to become abstinent, we will explore the use of zero-truncated negative binomial regression for count data to examine the main effects of treatment arm on changes in smoking rate at all assessment time-points.

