Monitoring for Adverse Events (AE) will be conducted by the study staff and the PI and co-investigators. Study staff will administer standardized assessments to evaluate mental health and QOL (BASIS-R and SF-12, respectively). Participants will be queried to provide open ended descriptions of any adverse event which occurred since the previous assessment. Should a report rise to the level of a potential Adverse Event, the decision on the course of action for the participant will be decided by [name] after review of the report. Participants will be monitored for the development of adverse events by administering these scales at 5 time-points during the study. In addition, both personnel and clients will be given contact information should they need to reach a member of the study between assessment time-points. The Research Team will clinically follow all subjects who are discontinued due to a serious adverse event until it resolves and becomes completely stable, unless a referral to another physician (i.e., specialist) is clinically indicated or requested by the subject. All AEs and SAEs will be documented on an Adverse Events Case Report Form. This information will, in turn, be reported immediately to all necessary regulatory committees. All serious adverse events will be reported within 24 hours to senior study staff. These events will be maintained in a unique data base and reviewed monthly by senior study staff.

[name] and staff RAs will be responsible for monitoring data integrity as data are collected. This includes ensuring that source documents exist for the data on the Case Report Forms, ensuring all fields are completed appropriately, all corrections are done according to GCPs and any inconsistencies/deviations are documented.

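### After early withdrawal, Section 6.4 names only a Week 52 assessment, although Week 36 is also a primary time point

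*Combined protocol and SAP*

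**What the plan says.** Section 6.4 gives one rule for outcome collection after early withdrawal: "Subjects who withdraw early will be contacted to complete a final visit (Week 52) to collect final evaluations and assess adverse events". The same paragraph lets the investigator end participation: "The Principal Investigator may withdraw subjects who violate the study plan, to protect the subject for reasons related to safety or for administrative reasons". It does not say whether the follow-up sentence reaches that second group. On numbers, it says "we expect that <15% of personnel and clients will withdraw from the trial or be lost-to-follow-up", with no split by cause, arm or timing.

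The time points are set elsewhere:

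- Aim 1, Section 7.2.1: "Although level of adherence at 36 and 52 weeks will represent our primary outcome variables".
- Aim 2, Section 7.2.1: "Although quit-rates at the end of 36 and 52 weeks will represent our primary outcomes".
- Aim 3, Section 7.1: "the analysis will use non-inferiority testing to compare mental health and QOL across ATTOC and UC at weeks 36 and 52".

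No section ranks Week 36 below Week 52. For Aim 2, Section 4.8.1 counts as smokers those who "do not provide self-report or CO data at the time-point", and Section 7.2 repeats this as the ITT rule. For Aims 1 and 3, Section 7.2 promises suitable missing-data methods without naming one.

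**The concern.** The text arranges to collect one of two equally primary time points from people who stop early, and is silent on the other. The silence matters only for those who stop before Week 36. For them, Aim 2 has a Week 36 result whatever happens, because the missing-data rule supplies one: smoking. An abstinent client who would have agreed to be seen is recorded as a smoker because nobody was told to ask. For Aims 1 and 3, the Week 36 questionnaires are simply missing.

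For clients this is avoidable. The intervention acts on the clinic, so leaving the study does not in itself take a client out of an ATTOC clinic, and the Week 36 outcome keeps its meaning. The argument is weaker for staff, whose use of the Dashboard (Section 4.7) is part of how ATTOC is delivered.

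At stake is whether the Week 36 and Week 52 comparisons rest on the same people, and whether the Week 36 contrast is distorted if early withdrawal differs between arms.

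**Working it through.** **1. What needs a Week 36 contact**

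| Outcome | Week 36 value if the person left earlier |
|---|---|
| Aim 1 S-KAP | Missing; a mixed model can use other visits |
| Aim 1 EHR and prescription data (4.8.1) | Available, unless authorization is revoked (10.5) |
| Aim 2 abstinence | Scored as smoking (4.8.1, 7.2) |
| Aim 3 BASIS-R, SF-12 | Missing; a mixed model can use other visits |
| Aim 3 hospitalization (4.7, 4.8.1) | Available from EHR and CBH, unless authorization is revoked; compared over 52 weeks (7.2.1) |

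A Week 52 timeline follow-back reaches back to the prior assessment (4.7), so it could cover the Week 36 days by recall. It cannot supply a CO reading at Week 36, so the client would still be scored as smoking.

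**2. Precision for Aims 1 and 3, starting from the plan's own figures**

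Aim 1 inputs (7.1): SD 0.87, 280 staff, 14 clinics, 80% power, α .05 taken as two-sided. With 15% lost, N = 280 × 0.85 = 238, or 119 per arm and 17 per clinic. Detectable difference = (t.975 + t.80 on 12 df) × 0.87 × √(2 × DE / n per arm), with DE = 1 + (m − 1) × ICC and m the number per clinic.

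| ICC | No loss: plan / recomputed | 15% loss: plan / recomputed |
|---|---|---|
| 0 | 0.32 / 0.317 | 0.34 / 0.344 |
| .05 | 0.44 / 0.443 | 0.46 / 0.462 |
| .10 | 0.54 / 0.540 | 0.56 / 0.555 |
| .15 | 0.62 / 0.623 | 0.63 / 0.635 |

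The plan's figures reproduce. Losing all 15% at Week 36 costs at most 0.344 − 0.317 = 0.027 on the 5-point scale.

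BASIS-R (SD 0.8, one-sided .025, normal approximation): 0.184 at ICC 0 and 0.494 at ICC .15 with 595 clients, against the plan's 0.19 and 0.50. With all 700 they are 0.169 and 0.490. The cost is again small and already in the plan.

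**3. Aim 2**

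With 350 clients per arm and DE = 1 + 49 × ICC, the detectable differences from a 2% usual-care rate are 4.2, 10.0, 14.9 and 19.4 points, against the plan's 4, 10, 15 and 19.

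Let w be the share of an arm that withdraws before Week 36 and is therefore scored as smoking. Assume that withdrawal is unrelated to quitting and that the stated rates are those under full ascertainment. Then recorded rate = true rate × (1 − w). The plan gives no w; the values below are assumed, capped at 15% (105 of 700 clients). True rates are 12% vs 2%, the plan's detectable difference at ICC .05. Odds ratio = [p1/(1 − p1)] / [p0/(1 − p0)].

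| w, ATTOC / UC | Recorded rates | Difference (points) | Odds ratio |
|---|---|---|---|
| 0 / 0 | 12.0% / 2.0% | 10.0 | 6.68 |
| 5% / 5% | 11.4% / 1.9% | 9.5 | 6.64 |
| 10% / 10% | 10.8% / 1.8% | 9.0 | 6.61 |
| 15% / 15% | 10.2% / 1.7% | 8.5 | 6.57 |
| 15% / 7.5% | 10.2% / 1.85% | 8.35 | 6.03 |
| 7.5% / 15% | 11.1% / 1.7% | 9.4 | 7.22 |

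Power at true rates of 6% vs 2%, ICC 0, 350 per arm: 0.772 with w = 0, then 0.749, 0.725 and 0.700 with w = 5%, 10% and 15% in both arms. With 15% in ATTOC and 5% in UC, the difference is 5.1% − 1.9% = 3.2 points and power 0.635. With the shares reversed, it is 5.7% − 1.7% = 4.0 points and power 0.802.

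**The case against.** The best defence is that Section 6.4 does not say that Week 52 is the sole contact, and nothing bars a Week 36 call. That is true, but staff following the text have an instruction for one visit and none for the other.

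Several further points stand and limit the concern:

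- A reader might infer that the Week 36 outcome is lost for Aims 1 and 3. It is not: hospitalization and the record-based adherence data need no visit, the mixed models can draw on a person's other visits (under a missing-at-random assumption), and departing staff may complete sessions early (6.3). What goes missing is the questionnaire scores.
- A reader might infer that the missing scores belong mainly to clients who did badly, which would favour non-inferiority in Aim 3. The documents do not support this. No section makes a psychiatric admission a ground for withdrawal. Section 8.1 promises clinical follow-up of "all subjects who are discontinued due to a serious adverse event until it resolves" and does not say that outcome assessment stops.
- A reader might take investigator-withdrawn people to be covered by the Week 52 rule. The wording leaves this open; if they are not covered, no outcome follow-up is stated for them.
- A reader might suppose that a visit held at withdrawal would be filed as Week 52. No such practice is described.
- The 15% is a ceiling that includes loss to follow-up, which a contact rule cannot repair, and withdrawal after Week 36, which does not matter here. On the planned odds-ratio scale, equal withdrawal barely moves the result (6.68 to 6.57), and no imbalance between arms is documented.
- A phone call alone does not rescue Aim 2, because a client without a CO reading is still scored as smoking.

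**Conclusion.** The point holds in a limited form. For people who stop before Week 36, the plan seeks the Week 52 assessment and provides for no Week 36 assessment, although both are primary. Clients among them become smokers at Week 36 by rule, and the Week 36 S-KAP, BASIS-R and SF-12 scores are missing.

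The effect on precision is small, and Aims 1 and 3 already allow for 15% loss. The concern is avoidable missing data and, above all, possible bias in Aim 2 if early withdrawal differs by arm. On the assumed 15% / 7.5% splits, an odds ratio of 6.68 would be recorded as 6.03 or 7.22, depending on which arm loses more; neither split is predicted by the documents.

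The fall from 10 to 8.5 points is an upper bound for equal withdrawal. It assumes that all 15% in both arms are withdrawals before Week 36, that they quit at the same rate as everyone else, and that all would have been recovered. If people who withdraw are mostly still smoking, or decline the visit, the recoverable part is smaller. This is a cheap improvement to make, not a flaw that invalidates the analysis.

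**What to change.** Revise Section 6.4 to state that:

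1. Participants who stop before Week 36 will be asked, unless they refuse further contact, to complete both the Week 36 and the Week 52 outcome assessments at their scheduled dates.
2. Questionnaires may be done by phone, as Section 6.3 already allows. Clients who report abstinence are asked for the in-person CO reading already provided for in Section 4.4; without it, the Aim 2 result stays at smoking.
3. Any assessment done at the time of withdrawal is recorded under its actual date.
4. The same outcome follow-up is sought from participants whom the investigator withdraws.

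This uses existing instruments, staff and payments. Under Section 12.3 the Week 36 payment is $20 for staff, and $20 plus $10 travel for clients. The ceiling, if all 15% left before Week 36 and all agreed, is 105 × $30 + 42 × $20 = $3,990, for visits already in the payment schedule. The downside is one extra contact for a minority, who may decline it.
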